5.8.4. Analysis of Vital Signs

The following definitions will be applied to vital signs parameters:

- Double-blind treatment period: The treatment period used for quantitative analysis in the double-blind period is defined as the day after the first study drug administration to the day of the last double-blind study drug injection + 7 days for Group A. For Group B, the treatment period is defined from the day after the first administration of double-blind study treatment to the day of the last administration of double-blind study treatment + 28 days for those patients not proceeding into the open-label treatment period, or up to the day of the first open-label study treatment administration for those patients proceeding into the open-label treatment period.
- Open-label treatment period: The treatment period used for quantitative analysis in the open-label study period is defined from the day after the first dose of open-label study treatment to the day of the last dose of open label study treatment + 28 days.

For respective treatment period (DBTP and OLTP), the vital sign actual values and change from baseline values obtained while sitting will be descriptively summarized at baseline and each post-baseline visit by at least patient number, mean, median, Q1, Q3, SD, minimum and maximum. Vital sign mean changes from baseline, with the corresponding SE, can be plotted at each visit in the case results warrant further investigation.

Individual patient vital sign measurements (regardless of sitting position) will be additionally evaluated by PCSV criteria, specifically identifying patients with at least one post-baseline measurement that meets the PCSV criteria within the TEAE period. The incidence of PCSVs at any time during the respective TEAE periods will be summarized regardless of the baseline level, and again according to the following baseline categories:

- Normal (according to PCSV criterion/criteria)/missing
- Abnormal according to PCSV criterion or criteria

Patient listings of vital sign measurements that meet PCSV criteria will be provided for the report appendix.

5.8.5. Analysis of 12-Lead ECG

The following definitions will be applied to ECG parameters:

- **Double-blind treatment period:** The treatment period used for quantitative analysis in the double-blind period is defined as the day after the first study drug administration to the day of the last double-blind study drug injection + 7 days for Group A. For Group B, the treatment period is defined from the day after the first administration of double-blind study treatment to the day of the last administration of double-blind study treatment + 28 days for those patients not proceeding into the open-label treatment period, or up to the day of the first open-label study treatment administration for those patients proceeding into the open-label treatment period.
- **Open-label treatment period:** The treatment period used for quantitative analysis in the open-label study period is defined from the day after the first dose of open-label study treatment to the day of the last dose of open label study treatment + 28 days.

For respective treatment period (DBTP and OLTP), ECG parameters will be described through an overall interpretation of ECG status (e.g. normal, abnormal [clinically significant (Yes/No)]). The count and percentage of patients with at least 1 abnormal post-baseline ECG during the respective TEAE period will be summarized according to the following baseline status categories:

- Normal/missing;
- Abnormal

Individual patient ECG measurements will be additionally evaluated by PCSV criteria, specifically identifying patients with at least one post-baseline measurement that meets the PCSV criteria within the TEAE period. The incidence of PCSVs at any time during the respective TEAE periods will be summarized regardless of the baseline level, and again according to the following baseline categories:

- Normal (according to PCSV criterion/criteria)/missing
- Abnormal according to PCSV criterion or criteria

Patient listings of ECG measurements that meet PCSV criteria will be provided for the report appendix.

5.8.6. Physical Exams

A list of patients with any clinically significant abnormality results will be generated.

5.9. Analysis of Other Variables

In general, for the double-blind period, the summary of results for other variables for patients in the double-blind SAF population will be presented by route of administration (Group A or Group B) and pooling the evinacumab dose regimens within each route of administration (Group A or Group B), with the intent to maximize efforts to identify potential safety signals. The treatment group data (individual evinacumab dose regimens and placebo) will also be presented with the intent to support the pooled dose regimens. No formal inferential testing will be performed. Summaries will be descriptive in nature.

For Group B, summaries of safety results for the open-label period will be presented for patients in the open-label SAF, by the total number of patients administered open-label study treatment (ie., 15 mg/kg IV), as well as by the patient subgroups of study treatment received in the DBTP (ie., 5 mg/kg IV, 15 mg/kg IV, or placebo). No formal inferential testing will be performed for either period. Summaries will be descriptive in nature.

All measurements, scheduled or unscheduled, fasting or not fasting, will be assigned to Global Analysis Windows ([Appendix 10.2](#)) in order to provide an assessment for all post-baseline visit.

Hs-CRP, HbA1c, and HDL-C parameters will be summarized for the number of patients with data, mean, SD, median, minimum, maximum, Q1 and Q3 by analysis visit during the treatment period. The medians (with Q1-Q3) will be plotted for hs-CRP. The means (+/-SE) will be plotted for HbA1c and HDL-C. In addition, HbA1C will be summarized at each visit by diabetic status as recorded in the medical history e-CRF page (regardless of the ongoing status). Applying the

PCSV criteria to HbA1c at any time during the TEAE period, the number of patients (and percentages) meeting the criteria will be summarized.

5.10. Analysis of Pharmacokinetic and Pharmacodynamic Variables

Descriptive statistics of concentrations of total evinacumab and total ANGPTL3 will be presented. For the determination of arithmetic means and descriptive statistics, individual concentration values below the LLOQ, will be set to zero. If geometric means are determined, individual concentrations values below the LLOQ will be imputed as LLOQ/2.

Plots of the mean concentrations (linear and log scales) will be presented by nominal sampling time. Plots of the individual concentrations (linear and log scales) will be presented by actual sampling time. In the linear-scaled plots, concentrations below the LLOQ will be set to zero; in the log-scaled plots, concentrations below the LLOQ will be imputed as LLOQ/2.

When appropriate, relationship between concentrations of evinacumab and LDL-C or other biomarkers may be evaluated descriptively.

5.11. Analysis of Anti-evinacumab Antibody Variables

The ADA variables described in Section 4.11 will be summarized by dose/cohort group in the ADA analysis set. Listings of ADA results and titers values presented by patient, time point, and study treatment received will be provided. Prevalence of treatment-emergent ADA will be assessed as absolute occurrence (N) and percent of patients (%), grouped by study treatment received.

The influence of ADA on drug concentrations will be evaluated. Assessment of impact of ADA on safety and efficacy may be provided.

Anti-drug antibody status and titer over the study duration may be classified as follows:

- Pre-existing immunoreactivity, defined as a positive ADA assay response at baseline, with all post-dose ADA results negative, or a positive assay response at baseline, with all post-dose ADA assay responses less than 9-fold over baseline titer levels.
- Treatment emergent - defined as any post-dose ADA positive response when baseline results are negative or missing.
 - Persistent - A positive result in the ADA assay detected in at least 2 consecutive post baseline samples separated by at least a 16-week post baseline period [based on nominal sampling time], with no ADA-negative results in-between, regardless of any missing samples
 - Indeterminate - A positive result in the ADA assay at the last collection time point analyzed only, regardless of any missing samples
 - Transient - Not persistent or indeterminate regardless of any missing samples
- Treatment boosted - defined as any post-dose ADA response that is at least 9-fold over baseline titer levels when baseline results are positive

- Titer category for subjects, by maximum ADA titer value:
 - Low (titer <1,000)
 - Moderate ($1,000 \leq \text{titer} \leq 10,000$)
 - High (titer >10,000)
- NAb status (positive or negative)

6. DATA CONVENTIONS

The following analysis conventions will be used in the statistical analysis.

6.1. Definition of Baseline for Efficacy/Safety Variables

Unless otherwise specified, the baseline assessment is programmatically as the last available measurement prior to the date of the first double-blind study treatment administration. For patients randomized and not treated, the baseline value is defined as the last available value prior to the date of randomization.

6.2. Data Handling Convention for Efficacy Variables

Rules for handling missing data for primary and secondary efficacy variables are described in Section 5.7.1 and Section 5.7.1.4.

6.3. Data Handling Convention for Missing Data

Missing data will not be imputed in listings. This section includes the methods for missing data imputation for some summary analyses, if necessary.

Date and Time of First/Last Study Treatment

Since the study drug is administered at the site, the date and time of study drug administration are filled in e-CRF. No missing data is expected. Date of first/last administration is the first/last start date of study drug filled in e-CRF.

Adverse Event

If the intensity of a TEAE is missing, it will be classified as “severe” in the frequency tables by intensity of TEAEs. If the assessment of relationship of a TEAE to the investigational product is missing, it will be classified as related to the investigational product.

When the partial AE date/time information does not indicate that the AE started prior to study treatment or after the TEAE period, the AE will be classified as treatment-emergent.

Medication/Procedure

No imputation of medication/procedure start/end dates or times will be performed. If a medication date or time is missing or partially missing and it cannot be determined whether it was taken prior or concomitantly or stopped prior to the first study treatment administration, it will be considered as concomitant medication/procedure.

Potentially Clinically Significant Value (PCSV)

If a patient has a missing baseline value, this patient will be grouped in the category “normal/missing at baseline.”

For PCSVs with 2 conditions, one based on a change from baseline value and the other on a threshold value or a normal range, with the first condition being missing, the PCSV will be based only on the second condition.

For a PCSV defined on a threshold and/or a normal range, this PCSV will be derived using this threshold if the normal range is missing; e.g., for eosinophils the PCSV is >0.5 giga/L or $>ULN$ if $ULN \geq 0.5$ giga/L. When ULN is missing, the value 0.5 should be used.

Measurements flagged as invalid by the laboratory will not be summarized or taken into account in the computation of PCSVs.

6.4. Visit Windows

Visit windows will be programmatically imposed on those efficacy and safety measures repeatedly collected over the course of the study. These visit windows are derived from the number of days in study, specifically assigning day ranges to represent the study assessment schedule provided in the protocol. Data analyzed by time point (including efficacy, laboratory safety data, vital signs, and ECG) will be summarized using the analysis windows given in [Appendix 10.2](#) (i.e. efficacy analysis windows for efficacy and global analysis windows for safety). These analysis windows will be applicable for all analyses, and they are defined to provide more homogeneous data for time point-specific analyses. If multiple valid values of a variable exist within an analysis window, the nearest from the targeted study day will be selected for analysis, unless otherwise specified. If the difference is a tie, the value after the targeted study day will be used. If multiple valid values of a variable exist within a same day, then the first value of the day will be selected when time is available, else the scheduled visit will be selected.

6.5. Unscheduled Assessments

For efficacy, safety laboratory data, vital signs, and ECG unscheduled visit measurements may be used to provide a measurement for a time point, including baseline, if appropriate according to their definitions. The measurements may also be used to determine abnormal values, AESIs, and PCSVs.

6.6. Pooling of Centers for Statistical Analyses

The randomization scheme was not stratified by center because the primary efficacy variable is centrally assessed and expected not to be influenced by the center when other factors such as diet are already controlled. Therefore, the center will not be added as factor in the primary analysis model.

6.7. Statistical Technical Issues

Not Applicable.

7. TIMING OF STATISTICAL ANALYSES

7.1. First Step: Group B Main Efficacy and Safety Analysis

The first analysis will be conducted when all Group B patients have been randomized and all data through week 24 has been collected and validated for these patients. This will consist of the final efficacy analysis of the primary and secondary endpoints for the Group B patients. The Group B safety analysis will be performed on all double-blind safety data and any open-label safety data collected and validated at the time of the first step analysis.

The results of the first analysis will not be used to change the conduct of the ongoing study in any aspect. This first analysis may be used for submission to health authorities.

Individuals involved in the first step analysis of the study will not be involved in the conduct of the study afterwards. Individual patient identification will not be released to anyone who is directly involved in the conduct of the study. The first step analysis process, the measures used to protect the blind and the integrity of the study, the communication plan, and the confidentiality agreement will be described in a separate document.

7.2. Second Step: Group A Main Efficacy and Safety Analysis

The second analysis will be conducted when all Group A patients have been randomized and all data through week 16 has been collected and validated for these patients. This will consist of the final efficacy analysis of the primary and secondary endpoints for the Group A patients. The Group A and Group B (open-label period) safety analyses will be performed on all safety data collected and validated at the time of the second step analysis.

Results of the second analysis will not be used to change the conduct of the ongoing study in any aspect. This second analysis may be used for submission to health authorities.

Individuals involved in the second step analysis of the study will not be involved in the conduct of the study afterwards. Individual patient identification will not be released to anyone who is directly involved in the conduct of the study. The second step analysis process, the measures used to protect the blind and the integrity of the study, the communication plan, and the confidentiality agreement, will be described in a separate document.

7.3. Third Step: Final Safety Analysis

The third analysis will be conducted at EOS and will consist of the final safety analysis through the follow-up period (week 39 for Group A and week 92 for Group B).

7.4. Additional Rules

Analyses methods and conventions described in the other sections of this SAP will be applied for all analyses as applicable. The following additional rules will apply for analyses performed at first and second step analyses:

- Any lipid assessments within efficacy analysis windows up to the week 24 visit for Group B and week 16 visit for Group A will be taken into account (may include few unscheduled lipid data soon after the cut-off date).

- Patients without end of treatment visit performed at the time of the cut-off date will be considered as ongoing and exposed up to the cut-off date. Therefore:
 - Patients who did not complete the respective treatment period nor prematurely discontinued the study treatment at cut-off date will be analyzed as “ongoing” in the disposition summary.
 - Their TEAE period and treatment period will end at the respective data cut-off date.
 - Their treatment duration will be derived by considering date of cut-off as last administration date.
- Analyses of number of administrations, and mean administration frequency will be performed up to the last administration reported in the e-CRF up to the cut-off date.
- AEs occurring, worsening or becoming serious after the cut-off date will not be included in the analyses. However, any available outcome before database lock, regardless of timing in relation to the cut-off date, of an adverse event starting prior to the cut-off date will be taken into account. Medications, treatment discontinuations/completions and deaths occurring after the cut-off date will not be included in the analyses.
- Post-treatment period, and post-study period are not applicable for ongoing patients. Analyses of post-study deaths and post-treatment medications will be performed for patients who either completed or prematurely discontinued the treatment before or at the data cut-off date.
- Analysis of status at last study contact and proportion of patients with insufficient follow-up will be provided for patients who either completed or prematurely discontinued the treatment before or at the data cut-off date.

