- Patient duration of open-label study treatment exposure in weeks defined as: (last open-label evinacumab treatment administration date +28 – first open-label evinacumab treatment administration date)/7. Unplanned intermittent discontinuations in study treatment will be addressed on a case-by-case basis, since this is expected to be a rare occurrence. Values will be rounded to one decimal place.
- Patient duration of open-label study treatment exposure in patient-years defined as: (last open-label evinacumab treatment administration date +28 – first open-label evinacumab treatment administration date)/365, regardless of unplanned intermittent discontinuations.
- The total number of open-label evinacumab treatment infusions by patient.
- The following categories will be used for treatment exposure at 4 week intervals: ≥ 1 day and < 4 weeks, ≥ 4 weeks and < 8 weeks, ≥ 8 weeks and < 12 weeks, ≥ 12 weeks and < 16 weeks, ≥ 16 weeks and < 20 weeks, ≥ 20 weeks and < 24 weeks, ≥ 24 weeks and < 28 weeks, ≥ 28 weeks and < 32 weeks, ≥ 32 weeks and < 36 weeks, ≥ 36 weeks and < 40 weeks, ≥ 40 weeks and < 44 weeks, ≥ 44 weeks and < 48 weeks, ≥ 48 weeks

Study treatment exposure variables combining DBTP and OLTP are listed below for all Group B patients who received evinacumab in the DBTP:

- Cumulative patient duration of evinacumab exposure in weeks defined as: double-blind treatment exposure plus open-label treatment exposure, regardless of unplanned intermittent discontinuations.

- Cumulative patient duration of evinacumab exposure in patient-years defined as: double-blind treatment exposure in patient-years plus open-label treatment exposure in patient-years, regardless of unplanned intermittent discontinuations.
- Cumulative total number of evinacumab treatment infusions by patient defined as: total number of double-blind infusions plus total number of open-label infusions.
- The following categories will be used for cumulative patient treatment exposure at 4 week intervals: ≥ 1 day and < 4 weeks, ≥ 4 weeks and < 8 weeks, ≥ 8 weeks and < 12 weeks, ≥ 12 weeks and < 16 weeks, ≥ 16 weeks and < 20 weeks, ≥ 20 weeks and < 24 weeks, ≥ 24 weeks and < 28 weeks, ≥ 28 weeks and < 32 weeks, ≥ 32 weeks and < 36 weeks, ≥ 36 weeks and < 40 weeks, ≥ 40 weeks and < 44 weeks, ≥ 44 weeks and < 48 weeks, ≥ 48 weeks and < 52 weeks, ≥ 52 weeks and < 56 weeks, ≥ 56 weeks and < 60 weeks, ≥ 60 weeks and < 64 weeks, ≥ 64 weeks and < 68 weeks, ≥ 68 weeks and < 72 weeks, ≥ 72 weeks, etc.

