5.6.1. Exposure to Investigational Product

Study treatment exposure in the DBTP and OLTP will be descriptively summarized for treatment duration and total number of infusions/injections as described in Section 4.6. Treatment duration and total number of infusions will be summarized using the number of patients with data, mean, SD, median, minimum and maximum.

Additionally, evinacumab dosing exposure for Group B will be summarized cumulatively across the study, combining DBTP and OLTP for patients who received evinacumab in the DBTP.

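### Interim open-label exposure for ongoing Group B patients runs 27 days past the data cut-off, because SAP 7.4 makes the cut-off the last dose and SAP 4.6 then adds 28 days

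*SAP*

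**What the plan says.** SAP 7.4 sets extra rules for the first and second analysis steps. A patient with no end-of-treatment visit by the cut-off "will be considered as ongoing and exposed up to the cut-off date". Three consequences follow, and two matter here:

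- On the observation periods: "Their TEAE period and treatment period will end at the respective data cut-off date".
- On exposure, the rule at issue: "Their treatment duration will be derived by considering date of cut-off as last administration date".

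Section 7.4 opens by keeping the rest of the plan in force: the methods and "conventions described in the other sections of this SAP will be applied for all analyses as applicable".

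SAP 5.6.1 says exposure is "summarized for treatment duration and total number of infusions/injections as described in Section 4.6". In SAP 4.6 the open-label formula starts from "last open-label evinacumab treatment administration date +28" and subtracts the first open-label administration date. The result is divided by 7 for weeks. The patient-years version ends "administration date)/365, regardless of unplanned intermittent discontinuations". Protocol 10.4.4.3 gives the same open-label formula in weeks. Durations are also grouped: "categories will be used for treatment exposure at 4 week intervals".

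None of these sections removes the 28 days, or caps the result, for a patient whose last administration date has been replaced by the cut-off.

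**The concern.** The 28 days in SAP 4.6 stand for the dosing interval that an actual infusion covers. Once the cut-off replaces the last infusion date, there need be no infusion at the start of that interval, yet the interval is still added. Duration then runs beyond the cut-off, although Section 7.4 says exposure stops there and ends the same patient's treatment period on that date.

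The error always goes towards more exposure. Long-term intravenous exposure is the stated reason for the open-label period (protocol 3.2.1 and 3.2.3). SAP 4.5 expects patients to be ongoing in that period at the first step, and SAP 7.1 and 7.2 allow the first- and second-step analyses to be submitted to health authorities. Cumulative exposure carries the same error for patients given evinacumab in the double-blind period (72 planned).

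**Working it through.** **Inputs.** Open-label infusions are scheduled every 28 days from study day 169 to day 477, with the end-of-open-label visit on day 505 (schedule of events, Tables 4 and 5). Group B has 108 planned patients (protocol 6.1). The formulas are those of SAP 4.6.

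**The plan's own figure.** For a completer, 477 + 28 − 169 = 336 days = 48.0 weeks. This matches the planned 48 weeks and covers days 169 to 504 inclusive.

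**Three ways to count an ongoing patient.** Let d be the days from first open-label infusion to cut-off, 0 to 335 while ongoing.

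- As written (7.4 with 4.6): d + 28
- Through the cut-off, both end days counted: d + 1
- Actual last dose + 28, dosing on schedule: 28 × floor(d/28) + 28

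**Excess per patient.** Against the cut-off, (d + 28) − (d + 1) = 27 days for every d (28 if the cut-off day is not counted). Against last dose + 28, the excess is d − 28 × floor(d/28), which is 0 to 27 days with mean 13.5.

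**Extreme cases.**

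- First infusion on the cut-off date (d = 0): 28 days = 4.0 weeks, against 1 day through the cut-off.
- Cut-off on day 504 (d = 335): 363 days = 51.9 weeks, against 336 days = 48.0 weeks.
- The result exceeds 48.0 weeks only when d + 28 > 336, so for d = 309 to 335 (days 478 to 504), 27 of 336 values.
- Cumulative, after a full double-blind period of 141 + 28 − 1 + 1 = 169 days: (169 + 363)/7 = 76.0 weeks for the day-504 patient, against (169 + 336)/7 = 72.1 for a completer.

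**Patient-years.** 27/365 = 0.074 and 13.5/365 = 0.037 per ongoing patient. The documents do not say how many would be ongoing, so a range is shown.

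| Patients ongoing | Excess against cut-off | Excess against last dose + 28 |
|---|---|---|
| 20 | 1.5 | 0.7 |
| 50 | 3.7 | 1.8 |
| 108 (ceiling) | 8.0 | 4.0 |

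**Mean open-label exposure.** Enrolment duration is not given either. The table assumes uniform enrolment, all patients entering the open-label period, no discontinuation, dosing on schedule, and a cut-off when the last patient reaches week 24. Days are counted whole.

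| Enrolment (weeks) | Share ongoing | Mean weeks to cut-off | Mean weeks, last dose + 28 | Mean weeks as written | Overstated against cut-off | Overstated against last dose + 28 |
|---|---|---|---|---|---|---|
| 26 | 100% | 13.1 | 15.1 | 17.0 | 29% | 12% |
| 52 | 92% | 26.0 | 27.7 | 29.5 | 14% | 6% |
| 78 | 61% | 33.3 | 34.5 | 35.7 | 7% | 3% |
| 104 | 46% | 37.0 | 37.9 | 38.8 | 5% | 2% |

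A later cut-off makes these percentages smaller.

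**Open-label 4-week categories.** floor((d + 28)/28) is one higher than floor((d + 1)/28) for 324 of the 336 values of d (96%). It equals the last dose + 28 category for all 336.

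**The case against.** The strongest reply is that Section 7.4 states its principle first, that exposure ends at the cut-off, and carries other conventions over only where applicable. It already cuts the 168-day adverse-event tail and the 28-day laboratory and vital-sign tail at that date, so a programmer could read the duration rule the same way and drop the 28 days. That reading is sensible, but the text does not state it. The rule changes one input to the formula and leaves the formula alone, so following it exactly gives the longer figure.

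A second reply is that 27 days is measured against the less favourable benchmark. The plan counts everyone else as last dose + 28. On that scale the mean excess is 13.5 days, no open-label category changes, and 4.0 weeks after a single infusion is normal. All of that is correct. The rule as written still meets that benchmark only when the cut-off falls on a dosing day, and otherwise exceeds it.

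A third reply concerns the fix. Stopping at the cut-off puts ongoing patients 0 to 27 days below last dose + 28, and one open-label category lower on 324 of 336 possible cut-off days. That also stands. It follows from the principle the SAP itself adopts for these patients, and it should be noted under the table.

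Finally, the consequences are limited. Infusion counts are reported beside duration, and no test or safety rate uses the overstated duration.

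**Conclusion.** The rule is wrong as written: it gives a figure that contradicts the principle stated just above it, and it generally exceeds last dose + 28 as well. The 27-day excess per ongoing patient follows from the formulas alone. The 0 to 27 day range (mean 13.5) also assumes dosing on schedule, with the mean taken over all possible cut-off days. The patient-year totals and percentages depend on the number ongoing, the enrolment duration and the cut-off date, none of which the documents give, so they are only a range.

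The effect is confined to descriptive open-label and cumulative exposure tables: at step 1, and at step 2 only for any Group B patient still on open-label treatment. Efficacy results, administration counts and the final third-step analysis are unaffected. So are open-label adverse-event rates per patient-year, because SAP 5.8.1 bases them on the TEAE period, which Section 7.4 ends at the cut-off. The sentence should be corrected, but it does not threaten the trial's conclusions.

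**What to change.** Replace the duration sentence in SAP 7.4 with: *For patients ongoing in the open-label period at the cut-off, open-label duration = (cut-off date − first open-label administration date + 1)/7 in weeks, or /365 in patient-years, with no 28-day extension. Cumulative exposure = double-blind exposure + this open-label exposure.*

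The day-504 patient then gets (504 − 169 + 1)/7 = 48.0 weeks, equal to the completer. A patient first infused on the cut-off date gets 1 day, which falls in the lowest category. Skipped doses are not deducted, in line with the patient-years formula in SAP 4.6.

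The cost is one SAP sentence and slightly smaller interim exposure figures. A table footnote should say that ongoing patients are counted to the cut-off and all others to last dose + 28, so that readers can allow for the difference.
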